14 ETHICS/PROTECTION OF HUMAN SUBJECTS

14.1 Ethical Standard

The site principal investigator (PI) will ensure that this trial is conducted in full conformity with principles of the Belmont Report: Ethical Principles and Guidelines for the Protection of Human Subjects of Research (National Commission for the Protection of Human Subjects of Biomedical and Behavioral Research [April 18, 1979]) and codified in 45 CFR 46, 21 CFR 50 and 21 CFR 56, as applicable. The PI will also ensure conformity with ICH E6 Good Clinical Practice, and applicable federal regulations, guidance, and guidelines for Good Clinical Practice and Clinical Trials with humans.

14.2 Institutional Review Board

Each site principal investigator will obtain IRB approval for this protocol to be conducted at his/her research site(s), and send supporting documentation to the DMID before initiating recruitment of subjects. The investigator will submit applicable information to the IRB/IEC on which it relies for the review, to conduct the review in accordance with 45 CFR 46, ICH E6 GCP, and as applicable, 21 CFR 56 (Institutional Review Boards) and 21 CFR 50 (Protection of Human Subjects), other federal, state, and local regulations. The IRB/IEC must be registered with OHRP [*OHRP-only* or *OHRP/FDA*] as applicable to the research. DMID must receive the documentation that verifies IRB/IEC-approval for this protocol, associated informed consent documents, and upon request any recruitment material and handouts or surveys intended for the subjects, prior to the recruitment and enrollment of subjects.

Any amendments to the protocol or consent materials will be approved by the IRB/IEC before they are implemented. IRB/IEC review and approval will occur at least annually throughout the enrollment and follow-up of subjects, and may cease if annual review is no longer required by applicable regulations. The investigator will notify the IRB/IEC of deviations from the protocol and reportable SAEs, as applicable to the IRB/IEC policy.

Each institution engaged in this research will hold a current Federalwide Assurance (FWA) issued by the Office of Human Research Protection (OHRP) for federally funded research.

14.3 Informed Consent Process

Informed consent is a process that is initiated prior to an individual agreeing to participate in a trial and continuing throughout the individual's trial participation. Before any study procedures are performed, informed consent will be obtained and documented. Subjects will receive a concise and focused presentation of key information about the clinical trial, verbally and with a written consent form. The explanation will be organized, and presented in lay terminology and language that facilitates understanding why one might or might not want to participate.

An investigator or designee will describe the protocol to potential subjects face-to-face. The key information about the purpose of the study, the procedures and experimental aspects of the study, risks and discomforts, any expected benefits to the subject, and alternative treatment will be presented first to the subject.

Subjects will also receive an explanation that the trial involves research, and a detailed summary of the proposed study procedures and study interventions/products. This will include aspects of the trial that are experimental, the probability for random assignment to treatment groups, any expected benefits, all possible risks (including a statement that the particular treatment or procedure may involve risks to the subject or to the embryo or fetus, if the subject is or may become pregnant, that are currently unforeseeable), the expected duration of the subject's participation in the trial, alternative procedures that may be available and the important potential benefits and risks of these available alternative procedures.

Subjects will be informed that they will be notified in a timely manner if information becomes available that may be relevant to their willingness to continue participation in the trial. Subjects will receive an explanation as to whether any compensation and any medical treatments are available if injury occurs, and, if so, what they consist of, or where further information may be obtained. Subjects will be informed of the anticipated financial expenses, if any, to the subject for participating in the trial, as well as any anticipated prorated payments, if any, to the subject for participating in the trial. They will be informed of whom to contact (e.g., the investigator) for answers to any questions relating to the research project.

Information will also include the foreseeable circumstances and/or reasons under which the subject's participation in the trial may be terminated. The subjects will be informed that participation is voluntary and that they are free to withdraw from the study for any reason at any time without penalty or loss of benefits to which the subject is otherwise entitled.

The extent of the confidentiality of the subjects' records will be defined, and subjects will be informed that applicable data protection legislation will be followed. Subjects will be informed that the monitor(s), auditor(s), IRB, NIAID, and regulatory authority(ies) will be granted direct access to the subject's original medical records for verification of clinical trial procedures and/or data without violating the confidentiality of the subject, to the extent permitted by the applicable

laws and regulations, and that, by signing a written informed consent form, the subject is authorizing such access.

Subjects will be informed that records identifying the subject will be kept confidential, and, to the extent permitted by the applicable laws and/or regulations, will not be made publicly available and, if the results of the trial are published, the subject's identity will remain confidential. Subjects will be informed whether private information collected from this research and/or specimens will be used for additional research, even if identifiers are removed.

Subjects will be allowed sufficient time to consider participation in this research trial, and have the opportunity to discuss this trial with their family, friends or legally authorized representative, or think about it prior to agreeing to participate.

Informed consent forms will be IRB-approved, and subjects will be asked to read and review the consent form. Subjects must sign the informed consent form prior to starting any study procedures being done specifically for this trial.

Once signed, a copy of the informed consent form will be given to the subject(s) for their records. The subject(s) may withdraw consent at any time throughout the course of the trial. The rights and welfare of the subject(s) will be protected by emphasizing to them that the quality of their medical care will not be adversely affected if they decline to participate in this study.

Study personnel may employ recruitment efforts prior to obtaining study consent if a patient-specific screening consent is on record or if the IRB has agreed that chart review is allowed without a fully executed screening consent. In cases where there is not a patient-specific screening consent on record, site Clinical staff may pre-screen via chart review and refer potential subjects to the Research staff. Research staff would obtain written consent per the standard informed consent process before conducting protocol-specific screening activities.

New information will be communicated by the site principal investigator to subjects who consent to participate in this trial in accordance with IRB requirements. The informed consent document will be updated, and subjects will be re-consented per IRB requirements, if necessary. Subjects will be given a copy of all informed consent forms that they sign.

14.3.1 Informed Consent/Assent Process (in Case of a Minor)

Investigators will follow IRB/IEC requirements for enrollment of minors in this study. Minors will be informed about the study to the extent understandable to the minor. Investigators or designee will conduct the consent process with the parent(s)/legal guardian, who will be given an IRB/IEC-approved permission form, which may be referred to as a consent form, to read, review, and sign prior to any study procedures. The parent(s)/legal guardian will be provided meaningful study information including a statement that this study involves research, the child may not benefit from the trial, and the study involves risk. The required elements will be clearly presented, including the purpose of the study, the experimental procedures, the potential risks

and discomforts, known adverse effects, possible benefits of the study for the subject, alternative therapies that may be beneficial, use and disclosure of private information, and other elements that are part of obtaining proper consent. The subject's parent(s)/legal guardian will be allowed sufficient time to discuss questions with the investigator.

The investigator or designee will describe in simplified terms the details of the study intervention/product, study procedures, risks and discomforts, benefits, and other consent elements, as appropriate. A separate IRB/IEC-approved assent form will be used for the minor, who may read and sign the form, or have it read to him/her prior to participation in study procedures. Assent may be obtained verbally or waived when approved by the IRB/IEC as appropriate to age. If a child declines to participate in the trial when assent is required by the IRB/IEC, the subject will not be enrolled even though the parents have provided permission. To ensure that consent is an ongoing process throughout the subject's participation in the study, the investigator and staff will review information as needed with the subject and the parent(s)/legal guardian and confirm that assent and permission are continuing. The permission and assent documents will be updated when new information is acquired that may impact the decision to continue in the study, and the subject's assent and the parent(s)/legal guardian's permission will be obtained, as applicable.

14.4 Exclusion of Women, Minorities, and Children (Special Populations)

This trial will be inclusive of all subjects who are ≥ 12 years of age and thus will follow all guidelines detailed in Subpart D – Additional Protections for Children Involved as Subjects in Research (45 CFR Part 46.401-409) who meet the Subject Inclusion/Exclusion Criteria, regardless of religion, gender, or ethnic background.

14.5 Subject Confidentiality

Subject confidentiality is strictly held in trust by the participating investigators, their staff, and the sponsor(s) and their agents. This confidentiality includes documentation, investigation data, subject's clinical information, and all other information generated during participation in the study. No information concerning the study or the data generated from the study will be released to any unauthorized third party without prior written approval of the DMID and the subject. Subject confidentiality will be maintained when study results are published or discussed in conferences. The study monitor or other authorized representatives of the sponsor or governmental regulatory agencies may inspect all documents and records required to be maintained by the investigator, including but not limited to, medical records (office, clinic, or hospital) and pharmacy records for the subjects in this study. The clinical study site will permit access to such records.

All records will be kept locked and all computer entry and networking programs will be carried out with coded numbers only and with password protected systems. All non-clinical specimens,

evaluation forms, reports, and other records that leave the site will be identified only by a coded number.

The study monitor, representatives from the NIH/DMID, representatives from Northwestern University and their affiliates, applicable regulatory authorities, such as the FDA and the IRB, representatives of Romark, L.C., or other authorized representatives of the sponsor may inspect all documents and records required to be maintained by the investigator, including but not limited to, medical records (office, clinic, or hospital) and pharmacy records for the subjects in this study. The clinical study sites will permit access to such records.

To protect privacy, we have received a Certificate of Confidentiality. With this Certificate, the researchers cannot be forced to release information that may identify the research subject, even by a court subpoena, in any federal, state, or local civil, criminal, administrative, legislative, or other proceedings. The researchers will use the Certificate to resist any demands for information that would identify the subject, except as explained below.

The Certificate cannot be used to resist a demand for information from personnel of the United States Government that is used for auditing or evaluation of federally funded projects, like this study, or for information that must be released in order to meet the requirements of the Federal Food and Drug Administration (FDA).

A Certificate of Confidentiality does not prevent the subject from voluntarily releasing information about themselves or their involvement in this research. If any person or agency obtains a written consent to receive research information, then the researchers may not use the Certificate to withhold that information.

The Certificate of Confidentiality does not prevent the researchers from reporting without the subject's consent, information that would identify the subject as a participant in the research project regarding matters that must be legally reported including: child and elder abuse, sexual abuse, or wanting to harm themselves or others.

14.6 Study Discontinuation

If the study is prematurely terminated by the sponsor, any regulatory authority, or the investigator for any reason, the investigator will promptly inform the study subjects and assure appropriate therapy or follow-up for the subjects, as necessary. The investigator will provide a detailed written explanation of the termination to the IRB/IEC. If any subject's private information will continue to be collected for this study, the IRB/IEC must approve a consent form with the study procedures, any risks and discomforts, and applicable elements, and the investigator or designee will re-consent the subjects as approved by the IRB/IEC.

In the event that the study is discontinued, subjects who were randomized to study drug can continue the use of the medication at the discretion of their clinician.

14.7 Costs, Subject Compensation and Research Related Injuries There is no cost to subjects for taking part in this trial.

Subjects may be compensated for their participation in this trial. Compensation will be in accordance with the local IRB's policies and procedures, and subject to IRB approval (no more than \$25/visit).

If it is determined by the participating site and the site principal investigator that an injury occurred to a subject as a result of the tests or treatments that are done for this trial, then referrals to appropriate health care facilities will be provided to the subject. Study personnel will try to reduce, control, and treat any complications from this trial. Immediate medical treatment may be provided by the participating site, such as giving emergency medications to stop allergic reactions to the study drug. No financial compensation will be provided to the subject by the participating site for any injury suffered due to participation in this trial

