5.3.5 Termination of Study

The study will be terminated if the DSMB determines that the study should be terminated based on safety concerns. If the study is terminated, the DSMB will be permitted to allow the longitudinal monitoring phase of the study to proceed. DMID and/or the IND holder may terminate the study at their sole discretion. Although the sponsor had every intention of completing this trial, it reserves the right to terminate this trial at any time for clinical or administrative reasons. Reasons for termination include, but not limited to, study closure due to DSMB review and recommendation and at the discretion of DMID.

If the study is prematurely terminated by the sponsor, any regulatory authority, or the investigator for any reason, the investigator will promptly inform the study subjects and assure appropriate therapy or follow-up for the subjects, as necessary. The investigator will provide a detailed written explanation of the termination to the IRB/IEC.

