6.6 Concomitant Medications/Treatments

Subjects may receive any therapy that is deemed appropriate to treat the signs and symptoms of Norovirus after randomization at the discretion of their treating provider except for nitazoxanide and oral immunoglobulin. This can include:

- Intravenous immunoglobulin
- Changes in immunosuppression
- Anti-motility agents

Any treatment utilized should be included on the concomitant medications at the time of enrollment. Any concomitant medication pre- or post-randomization that is being used to treat the signs or symptoms of Norovirus should be marked as such on the Case Report Form for the entire duration of the study. Likewise, any change to immunosuppressive therapy would have a

note in the Case Report Form noting if the change was made because of elevated drug levels, for treatment of Norovirus or for other purposes. Concomitant medications will be collected through visit 12 (Day 180 after initial dose of study treatment) or early termination, whichever occurs first. If the Investigator learns that the subject has taken a prohibited medication (see inclusion/exclusion criteria) prior to the last dose, the Investigator will contact the DMID Medical Officer and CPM for instructions regarding the subject's continuation in the study.

Medications that might interfere with the evaluation of the investigational product should not be used unless absolutely necessary.

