7.1 Screening/Baseline/Treatment Phase

Any subject ≥ 12 years of age, recipient of a solid organ or hematopoietic stem cell transplant with a positive test for Norovirus within 7 days as part of routine clinical care will be approached to participate in the study. Once consent is obtained, then laboratory testing and medical history will be reviewed to determine eligibility unless local IRB waiver allows to review data prior to consent. Assessment required for eligibility may not be measured more than twice.

a. Screening/Enrollment/Baseline

- Consent/Assent will be reconfirmed with eligible subjects, consistent with local IRB policy for consent and assent of subjects.
- Subject and their chart will be reviewed to collect a medical history, concurrent medications.
- Urine pregnancy test will be obtained from women of childbearing potential. Results must be known and negative prior to dosing.
- WBC, TLC (Total Lymphocyte Count) Hb, Platelets (Derived from Complete Blood Count -within 3 days of enrollment).
- Creatinine, Alk Phos, AST, ALT, BUN, Bilirubin (Derived from Complete Metabolic Panel-within 3 days of enrollment).
- T Cell Subsets will be drawn unless CBC shows an ALC <100 .
- Samples to be sent to the central laboratory are collected and processed:
 - Buccal swab and saliva samples for secretor assay.
 - Stool for quantitative Norovirus RT-PCR and sequencing.
 - Stool for other pathogen testing.
 - Stool for Norovirus-specific IgA, IgG, and IgM studies.
- Serum for quantitative Norovirus-specific IgA, IgG, and IgM and total IgG.
- Randomization.
- Vital signs will be obtained (pulse, temperature, BP, respiration, height and weight).
- Weekly Recall Packet will be administered.
- Detailed Subject Reported Outcome and Severity Score Assessment.
- Physical examination will be performed.

- Plastic bag with two 30-count bottles of study product will be dispensed to the subject. The first dose of study product (nitazoxanide or placebo) will be given by the study team.

The study product (nitazoxanide or placebo) will be taken by the subject twice daily for 28 days.

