9.2 Methods and Timing for Assessing, Recording, and Analyzing Safety Parameters

9.2.1 Adverse Events

ICH E6 defines an AE as any untoward medical occurrence in a patient or clinical investigation subject administered a pharmaceutical product regardless of its causal relationship to the study treatment. FDA defines an AE as any untoward medical occurrence associated with the use of a drug in humans, whether or not considered drug related.

An AE can therefore be any unfavorable and unintended sign (including an abnormal laboratory finding), symptom, or disease temporally associated with the use of medicinal (investigational) product. The occurrence of an AE may come to the attention of study personnel during study visits and interviews of a study recipient presenting for medical care, or upon review by a study monitor

Unsolicited clinical AEs are those non serious AEs that are **not** being collected as clinical outcome measures. For this study, unsolicited clinical AEs to be captured on the appropriate case report form, will be only those clinical AEs that meet either of the following criteria through 60 days:

- Result in modification in the administration of the study drug (nitazoxanide or placebo).
- Result in discontinuation of the study drug (nitazoxanide or placebo).

The following solicited safety laboratory parameters will be assessed on Day 7, 28 and 60: WBC, Hemoglobin, Platelet count, Creatinine, Alkaline Phosphatase, ALT, AST, BUN and Bilirubin. Additional laboratory parameters performed as part of the CBC and complete metabolic panel results need to be recorded in the source document with the evaluation of the site physician. Those additional laboratory value will need to be reported as AE only if clinically significant and not attributable to Norovirus infection or underlying SOT/HSCT medical conditions.

Abnormal values observed in the clinical laboratory assessment that are conducted by the clinical team outside the study visits, will be reported as AE only if the site physician assess that the laboratory value is clinically significant and not attributable to Norovirus infection or underlying SOT/HSCT medical conditions. The evaluation should be recorded in the source documents.

Laboratory AEs will be reported as defined in section 9.2.3.

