9.5 Halting Rules

Further enrollment will be halted for DSMB review/recommendation if any of the following are reported through Day 60:

- Two or more subjects experience a study product-related SAE.
- ≥ 4 subjects experience the same severe (Grade 3) study product-related unsolicited AE until 80 subjects enrolled or $\geq 5\%$ or more subjects experience the same severe (Grade 3) study product-related unsolicited AE after 80 subjects have been enrolled.
- ≥ 4 subjects experience the same severe (Grade 3) study product-related safety laboratory AE until 80 subjects enrolled or $\geq 5\%$ or more subjects experience the same severe (Grade 3) study product-related safety laboratory AE after 80 subjects have been enrolled.

Further enrollment will be halted for DSMB review/recommendation if the ratio of each clinical adverse outcome incidence rate per subject between the study arms is two or higher through Day 180:

- Death: Minimum of 4 or more subjects experience death in all study arms.
- Hospitalization: Minimum of 10 or more subjects experience hospitalization in all study arms.
- Graft rejection: Minimum of 5 or more subjects experience graft rejection in all study arms.
- Graft loss: Minimum of 5 or more subjects experience graft loss in all study arms
- Renal insufficiency, defined as a 20% or greater increase in serum creatinine relative to screening/enrollment/baseline value: Minimum of 10 or more subjects experience renal insufficiency in all study arms.

DMID retains the authority to suspend additional enrollment and study interventions/administration of study product during the entire study, as applicable.

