The DSMB may also be convened for an ad hoc meeting. An Ad hoc meeting is an unplanned meeting that is called for a specific purpose such as when a study halting rule is met. The meeting can be requested by any party with the responsibility of overseeing the trial (such as the PI, DSMB, DMID, industry collaborator). In the case of an ad hoc meeting, the DSMB may request special reports on an as-needed basis.

If the study is discontinued, subjects will not receive study product and, follow-up visits for safety would continue.

Additional data may be requested by the DSMB, and interim statistical reports may be generated as deemed necessary and appropriate by DMID. The DSMB may receive data in aggregate and presented by treatment arm. The DSMB may also be provided with expected and observed rates of the expected AEs in an unblinded fashion, and may request the treatment assignment be unblinded for an individual subject if required for safety assessment. The DSMB will review grouped and unblinded data in the closed session only. As an outcome of each review/meeting, the DSMB will make a recommendation as to the advisability of proceeding with study investigational product (as applicable), and to continue, modify, or terminate this trial.

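### Protocol 14.6 lets medication continue after study discontinuation with no safety exception and no stated source; read literally, it conflicts with 9.6.2

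*Protocol*

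**What the plan says.** Protocol 14.6 (Study Discontinuation) opens with premature termination by the sponsor, a regulatory authority or the investigator, for any reason. Its last sentence says that on discontinuation "subjects who were randomized to study drug can continue the use of the medication at the discretion of their clinician". The clinician's discretion is the only condition.

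Protocol 9.6.2 (DSMB) addresses the same event: "If the study is discontinued, subjects will not receive study product and, follow-up visits for safety would continue".

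Protocol 5.3.5 (Termination of Study) makes safety an explicit ground: "The study will be terminated if the DSMB determines that the study should be terminated based on safety concerns". On what may go on afterwards it says "If the study is terminated, the DSMB will be permitted to allow the longitudinal monitoring phase of the study to proceed". Section 7 defines that phase as Days 29 to 180, after the treatment phase.

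Other sections bear on study product when participation or the study ends:

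- 5.3.3 lists a sponsor or local regulatory decision to stop the study among the reasons for withdrawal and for ending study product administration.
- 6.4 has unused product disposed of under the Manual of Procedures (MOP) at completion or termination, with final disposition set by the sponsor.
- 7.4 has a subject who is terminated from the study come back within 7 days and hand in unused medication.
- 9.5 adds a general power: "DMID retains the authority to suspend additional enrollment and study interventions/administration of study product during the entire study, as applicable".

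**The concern.** Two sections start from the same event and, taken at face value, tell sites different things. One says no study product. The other lets the medication continue if the clinician agrees. Neither cites the other, and nothing in the Protocol or SAP says which prevails.

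The case that matters is a safety stop. A site that relied on 14.6 alone could let subjects go on taking a blinded product that the DSMB had just judged unsafe to continue. No new supply would be needed, because 7.1 provides at baseline that "Plastic bag with two 30-count bottles of study product will be dispensed to the subject", and 6.2 confirms that ambulatory subjects hold both bottles. What is at stake is subject protection and a clear instruction to sites, not the trial's inference.

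**Working it through.** The check is mainly textual. The plan states no figure on this point to reproduce.

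**Step 1: trigger.** Both sentences are conditioned on the study being discontinued. The 9.6.2 sentence sits among the DSMB provisions. Section 14.6 is general, and its opening is not limited by reason. Because 5.3.5 counts closure on DSMB review and recommendation among the reasons for termination, a safety stop falls within 14.6 as written.

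**Step 2: what is permitted.** Section 9.6.2 bars study product. Section 14.6 permits continuing the medication and names no source, duration or safety exception. The conflict is direct if the medication means trial tablets. If it means marketed nitazoxanide, the conflict over study product disappears but the missing safety exception remains.

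**Step 3: who is covered.** Section 14.6 covers subjects randomized to study drug. In 9.2.1 that term means nitazoxanide or placebo, while 6.1.2 uses a similar phrase for the active tablet alone. On the first meaning the qualifier excludes nobody. On the second, the clinician would need to know the assignment. Section 5.3.4 lets a site request unblinding only to manage an adverse event, and 14.6 provides no other route.

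**Step 4: which section is out of line.** Sections 5.3.3, 6.4 and 7.4 all lean towards stopping, disposal or return, and 5.3.5 mentions only longitudinal monitoring as able to proceed. Each has limits: 7.4 is written for an individual subject's termination, 6.4 defers detail to the MOP (not among the documents reviewed), and 5.3.5 is silent on dosing rather than prohibiting it. Together they still make 14.6 the outlier.

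**Step 5: scale per subject.** Inputs are 56 scheduled doses at two per day (section 7) and 2 × 30 = 60 tablets dispensed (6.2, 7.1). For *d* completed treatment days, scheduled doses left = 56 − 2*d* and tablets in hand = 60 − 2*d*.

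| Stop after | Scheduled doses left | Days of dosing left | Tablets in hand |
|---|---|---|---|
| 7 days | 56 − 14 = 42 | 21 | 60 − 14 = 46 |
| 14 days | 56 − 28 = 28 | 14 | 60 − 28 = 32 |
| 21 days | 56 − 42 = 14 | 7 | 60 − 42 = 18 |

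This assumes an ambulatory subject, every dose taken, no repeat dose after vomiting, and the 56-dose cap still in force.

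**Step 6: effect on the analysis.** The per-protocol adherence threshold is 0.75 × 56 = 42 doses, reached after 21 days. A subject stopped earlier would miss it, but 9.6.2 as written already has that effect. Sample size, power, alpha and the primary analysis do not depend on which rule applies.

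**The case against.** The strongest reply is that the two sections can be read together. Section 9.6.2 speaks of study product, the trial's own tablets. Section 14.6 speaks of the medication and leaves it to the subject's clinician rather than the investigator. Nitazoxanide is marketed (2.1), and section 7 already uses commercial stock for use beyond Day 28. It would be odd to let patients continue placebo as care. On this view 14.6 means later prescribed treatment. In addition, for a DSMB stop, 9.6.2 is the more specific rule.

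Much of this stands. It makes the problem an unresolved ambiguity rather than a proven contradiction. It does not dispose of the point, because 14.6 does not state that meaning, the commercial-stock rule was written for use after Day 28 rather than for discontinuation, and the safety exception is missing on either reading. Nor does it help to read 9.6.2 as barring only further dispensing. Ambulatory subjects already hold the full supply, so the rule would then do nothing for them.

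A reader might go further and infer that 9.6.2 is the only text between subjects and continued trial tablets after a safety stop. The documents do not support that: 5.3.3, 6.4 and 7.4 point the same way as 9.6.2, and the sponsor can suspend administration under 9.5. The tablets-in-hand scenario requires a site to disregard all of these.

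**Conclusion.** The point holds as a minor drafting inconsistency with a safety aspect. The last sentence of 14.6 lacks a safety exception and a stated source of drug. Taken literally, it permits exposure that 9.6.2 forbids. The risk is limited by the other provisions and by the sponsor's suspension power. No analysis is affected.

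The table shows what one subject could hold, not what happened. SAP 6.2 and 6.6 report that the study stopped for enrollment reasons after 31 subjects had enrolled. A reader might infer that subjects in this trial took product after the stop, or were harmed. The documents do not show that; the number affected is unknown and may be zero.

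A reader might also conclude that nitazoxanide should be barred after any discontinuation. That goes too far. The limits in 6.6 and section 7 are in-trial rules. Applying them after a non-safety stop would restrict a marketed drug for ill transplant recipients when no trial purpose remained.

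The conclusion rests on the Protocol and SAP alone. The MOP might contain a clearer instruction.

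**What to change.** Replace the last sentence of 14.6 with:

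> If the study is discontinued, study product stops for all subjects in both arms, unused product is returned by subjects and handled under section 6.4, and safety follow-up continues as in section 9.6.2. Unless the study was stopped for a safety concern, a subject's clinician may afterwards prescribe nitazoxanide from commercial stock.

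Do not carry the in-trial limits over to care after a non-safety discontinuation. These are the rule in 6.6, which allows therapy "at the discretion of their treating provider except for nitazoxanide and oral immunoglobulin", and the requirement in section 7 that the local investigator attest medical urgency after Day 28.

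The cost is one sentence, and no analysis rule changes. Because the study has already stopped, an amendment may now have little prospective use. In that case the clinical study report could state which rule sites followed and whether any study product was taken after the stop.
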